8.3.2 Mental health investigations

Ecological momentary assessment

During the measurement week, participants will be asked to fill out the eEMA questionnaire in the Leuven mPath app (or a similar platform meeting European privacy standards) 5 times a day on set times. Participants will receive a pop-up on their smartphones and will have a window of 1 hour to fill in the questionnaire. During this 1-hour window, participants will get multiple reminders to fill in the questionnaire. The questionnaire consists of multiple questions that gather information on current mood/feelings divided into multiple dimensions: positive affectivity, negative affectivity, energetic arousal and cognition. A 7-point rating scale will be used to answer the questions. To minimize the burden of this repeated questionnaire, the time needed to fill out the questionnaire is minimised/limited to approximately 4 minutes.

Subjective sleep quality

As an addition to the eEMA, two questions will be added to the morning questionnaire, one about general sleep satisfaction and one about the participants rested feeling.

Emography

Objective emotional arousal and stress will continuously be measured by the Cardiowatch 287-2 (Corsano Health, The Hague, the Netherlands) through electrodermal activity (measured by EDA and GSR).

8.3.3 Clinical test/procedures

Anthropometric measurements

Weight, height, and waist and hip circumference will be measured with a scale and measure in the research center which will be the same for all participants. Weight will be measured with the person dressed in light clothing and without shoes. Height will be measured with the person in standing position and wearing no shoes. Waist circumference will be measured at the midpoint between the lowest rib and the top of the iliac crest with a non-elastic tape and in standing position. Hip circumference will be measured at the widest part of the hip with a non-elastic tape and in standing position.

Body composition

Body composition will be assessed with bioelectrical impedance analysis (BIA, Omron BF508, Omron Healthcare Inc., Kyoto, Japan, or a similar device). This device can measure total body water, extracellular water, and intracellular water. The subject should be in a supine position for four minutes before the start of the measurement. Throughout the measurement the participants' arms and legs should be slightly apart and the subject should remain motionless. The measurement will last approximately one minute.

Hand grip strength

The handgrip strength measurement will be performed three times with the left hand and three times with the right hand using a hand dynamometer. This test will be performed with the participants sitting in a chair with armrests in an upright position with arms by their sides and the elbows at a 90-degree angle.

4 meter walking test

This test assesses gait speed. Participants are instructed to walk a distance of four meters at their normal pace. The time the individual needs to cover 4 meters is measured. Gait speed of longer than 5 seconds to walk 4 meters (0.8 m/s) suggests an increased risk of frailty and the need of further clinical review.

Resting blood pressure

After a 10-minute rest, systolic and diastolic blood pressure will be measured two times with a 2-minute interval on the dominant arm by trained staff members using a validated blood pressure device.

Continuous heart rate monitoring and heart rate variability

Participants will wear the Corsano Cardiowatch 287-2 (Corsano Health, The Hague, the Netherlands) wrist band on their right wrist continuously during the study period. The wristband is multifunctional and is waterproof. Participants will wear the wrist band 24 hours a day. The HR is measured using a PPG (photoplethysmogram, i.e., optically obtained volumetric measurement) and ECG. The manufacturer supplies the algorithm for converting the PPG/ECG signals into a set of HR values. All data from the Cardiowatch is available real time and is transferred from the watch to the smartphone using a clinical trial app, developed by the provider, which allows the researcher to retrieve live vital sign data while conducting a blinded study. From the app, it will be uploaded to the output server through a HIPAA/AVG compliant cloud service.

Core body temperature

Core body temperature will be continuously measured by the Cardiowatch 287-2. This parameter will be derived through an algorithm of combined data from Heatflux sensor and PPG signal. Diurnal patterns of core body temperature as well as the time of lowest daily temperature will be derived from this data.

Breathing rate and oxygen saturation

Breaths per minute count and oxygen saturation (%SpO₂) will also be derived from the Cardiowatch 287-2. Data will continuously be measured throughout the study period.

Objective sleep quality

Objective sleep quality will be monitored with the Withings Sleep Analyzer (Withings, Issy-les-Moulineaux, France) and an accelerometer (Corsano Cardiowatch 287-2 (Corsano Health, The Hague, the Netherlands), see text below). Prior to the study, the Withings Sleep Analyzer will be installed in the participants bed. A smart phone is required to set-up the device and the devices must be connected to a Wi-Fi to be able to send data to the cloud. After set-up no link to the smartphone is required. The device must be connected to power.

Objective physical activity

To monitor objective physical activity, Raw accelerometry will be derived from the Corsano Cardiowatch 287-2 (Corsano Health, The Hague, the Netherlands) on their right wrist during the entire study period. Raw data will be collected at 32Hz and will be derived from the wristband similar to the variable heart rate monitoring and HRV.

Food capturing

Participants will log their daily food intake during each measurement week by using a food diary that will be distributed prior to the start of the study. Frequency and timing of food intake will be assessed.

8.3.4 Invasive procedures

Melatonin assessment

On day 13 of all interventions (second-last day of the measurement week), participants will be asked to perform/collect 7 buccal swabs in a time range of 5 hours prior to bedtime to 1 hour after bedtime to measure the melatonin pattern DLMO. This measurement will be done according to the standard protocol from Chron@Work (Groningen, The Netherlands) in dim light conditions. (43) Participants will be carefully instructed beforehand on the procedure

Blood samples

A total of 62 ml blood will be sampled during the total study period (see **Table 8.2**). For screening purpose, we will sample 3.5 ml (nonfasting) blood for direct measurements of thyroid function (TSH, fT4), electrolytes (sodium, potassium), kidney function (eGRF/creatinin), liver function (AST, ALT, gammaGT by the Central Clinical Haematology Laboratory (CKHL) of the Leiden University Medical Center. At screening and baseline (and subsequently also after each intervention) will collect one 2 ml sample of venous blood in a vacutainer on EDTA. This sample will be used for direct measurement of haemoglobin, hematocrite, erythrocytes, MCV, MCH, MCHV, thrombocytes, leukocytes (neutrofile granulocytes, lymfocytes, eosinofile granulocytes, basofile granulocytes, monocytes) by the Central Clinical Haematology Laboratory (CKHL) of the Leiden University Medical Center, as well as for direct measurement of HbA1c the Department of Clinical Chemistry and Laboratory Medicine (CKCL) of the Leiden University Medical Center. For each participant, at baseline, and after each of the three interventions, we sample 3.5 ml (fasted) blood for batch measurements after completion of the study of: Insulin, glucose, eGRF/creatinin, Hs-CRP, Gamma GT, ASAT, ALAT, TSH, and ft4. In addition, for each participant, we will also collect after each of the three interventions: 1 x 2.5 ml Paxgen tubes (for isolation of RNA and measurement of clock gene expression) and 1x 2 ml EDTA (for metabolomics and proteomics). In addition, for each participant, after each of the three interventions, we will collect 2x 3.5 ml serum for Biobanking purposes. Moreover, residual biomaterial from this study that has not been used in above stated analysis will be transferred to the LUMC Biobank if permission is given by the participant. The regulations of the LUMC Biobank will be applicable.

Table 8.2. Overview of blood sampling

Sampling periods (number)	Tubes (type)	Tubes (number, volume)	Blood volume (total)	Type Biomaterial	Measured parameters
Screening	Serum	1x 3.5 ml	3.5 ml	serum	TSH, fT4, sodium, potassium, eGFR/creatinin, CRP, Gamma GT, ASAT, ALAT
Screening	EDTA	1x 2 ml	2 ml	plasma	HbA1c, Hematology (direct)
Baseline, and after each of the three interventions (4)	EDTA	1x 2 ml	8 ml	plasma	HbA1c, Hematology (direct)
Baseline, and after each of the three interventions (4)	Serum	1x 3.5 ml	14 ml	serum	Insulin, glucose, eGFR/creatinin, Hs-CRP, Gamma GT, ASAT, ALAT, TSH, ft4(in batch)
After each of the three interventions (4)	Paxgene	1x 2.5 ml	7.5 ml	RNA	Gene expression clock genes (in batch)
After each of the three interventions (4)	EDTA	1x 2 ml	6 ml	plasma	Metabolomics and proteomics (in batch)
After each of the three interventions (4)	Serum	2x 3.5 ml	21 ml	serum	Biobanking
Total amount of blood			62 ml		

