10.2 Secondary study parameter(s)

Secondary endpoints include changes in:

Biological clock function

- Clockgene expression
- Core body temperature (°C)
 - Diurnal pattern
 - Time of lowest temperature
- Melatonin
 - Dim light melatonin onset (DLMO)

Physiological parameters

- Heart rate
 - Diurnal pattern
 - Average
 - Resting heart rate
 - Minimum/peak heart rate (5 and 95 percentile)
- Heart rate variability (HRV)
- Breathing rate
- Oxygen saturation (SpO2)

Mental health

- Subjective mood
 - Diurnal pattern of:
 - Positive affectivity
 - Negative affectivity
 - Energy
 - Fatigue

- Cognition
- (objective) Electrodermal activity (emotional arousal and stress)

Behavioural factors

- Food intake
 - Frequency
 - Timing
- Habitual sleep (**Table 8.1**)
 - Sleep latency (min)
 - Duration (min)
 - Efficiency (%)
 - Sleep phases (%, min)
 - Awakenings at night (x, min)
 - Rested feeling (subjective, 0-7)
 - General satisfaction with sleep (subjective, 0-7)

Biochemistry

- Glucose metabolism
- Inflammatory markers
- Liver function
- Kidney function
- Thyroid function
- Bone metabolism markers
- White blood cell count

Changes between active morning and active evening will be assessed. Diurnal patterns will be calculated through the hourly mean level of for example glucose and will be displayed for each condition. Additionally, we will perform sensitivity analysis for both the primary endpoint as all secondary endpoints by analyse the changes between the sedentary period & active morning, and the sedentary period & active evening. Assuming the data is normally distributed, a paired t-test will be used for all analyses and data will be shown in as mean difference, SD, and p-value.

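### Clock-gene expression comes from an RNA tube with no cell separation described and is compared without using the white-cell differential measured at the same time points; a supportive analysis adjusted for it should be added.

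*Combined protocol and SAP*

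**What the plan says.** Section 8.3.4 collects, for each participant after each of the three interventions, "1 x 2.5 ml Paxgen tubes (for isolation of RNA and measurement of clock gene expression". Table 8.2 gives the biomaterial as RNA and the measurement as "Gene expression clock genes (in batch". Neither place describes separating cell types before the RNA is isolated.

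The same section provides a differential white-cell count: "At screening and baseline (and subsequently also after each intervention) will collect one 2 ml sample of venous blood in a vacutainer on EDTA". That tube is measured directly for, among other things, "leukocytes (neutrofile granulocytes, lymfocytes, eosinofile granulocytes, basofile granulocytes, monocytes". A differential therefore exists at every time point that has an RNA tube.

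Section 10.2 lists "Clockgene expression" under Biological clock function and, separately under Biochemistry, "White blood cell count". The contrast is stated as "Changes between active morning and active evening will be assessed", with the sedentary period against each active period as sensitivity analyses. If the data are normally distributed, "a paired t-test will be used for all analyses and data will be shown in as mean difference, SD, and p-value". No covariate, transformation or link between the differential and the expression data is given, and section 10.3 (other study parameters) is marked not applicable.

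**The concern.** RNA from blood in which the cells have not been separated gives an average over neutrophils, lymphocytes, monocytes and other cells, weighted by how many of each are present. That average can move because expression changes inside cells, or because the proportions change. Only the first is a change in clock function, which is how the protocol classes the endpoint.

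Pairing removes stable differences between people. It does not remove a within-person shift in cell mix between conditions. The design leaves a possible route to one: sessions run 10:00–11:00 in one condition and 19:30–20:30 in the other (section 5.1.1). If blood is drawn at a fixed clock time before the next session, the time since the last session differs by 9.5 hours between conditions. The sedentary contrasts compare recent exercise with none.

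If such a shift occurred, the planned test could show a clock-gene difference with no change inside any cell. The differential needed to look into this is already collected but has no role in the analysis of expression.

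**Working it through.** **The plan's own figure.** The documents give no sample size or SD for clock-gene expression. The only stated figure is for the ISI (section 4.4): difference 2.6, SD 5.4, so 2.6/5.4 = 0.481. A paired t-test at two-sided 0.05 with n = 36 has power 0.802, and 36/0.9 = 40. The plan's numbers reproduce. Only n = 36 is carried forward.

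**Assumed inputs, because the documents give none.** Neutrophils are 60% of white cells in one condition and 62%, 65% or 70% in the other. Expression per neutrophil is q times that in other white cells, with q = 0.25, 0.5, 2 or 4. Expression inside every cell is unchanged. The SD of paired differences in natural-log expression is 0.2 or 0.3. The test is two-sided at 0.05; section 10.2 states no level of its own.

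**Step 1, apparent change.** With neutrophil fraction f, measured expression is f × q + (1 − f).
- Example, q = 0.5: 0.60 × 0.5 + 0.40 = 0.700 and 0.65 × 0.5 + 0.35 = 0.675. The ratio is 0.964, a change of −3.6% (log −0.036).
- Example, q = 0.25: 0.550 falls to 0.5125, a change of −6.8% (log −0.071).

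**Step 2, rejection rate.** The noncentral t with 35 degrees of freedom and noncentrality (log change / SD) × √36 gives the chance that the paired t-test is significant.

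| Expression ratio | Shift (points) | Apparent change (q below 1 / q above 1) | Significant, over both directions and SD 0.2–0.3 |
|---|---|---|---|
| twofold | 2 | −1.4% / +1.3% | 6–7% |
| twofold | 5 | −3.6% / +3.1% | 9–19% |
| fourfold | 5 | −6.8% / +5.4% | 17–54% |
| fourfold | 10 | −13.6% / +10.7% | 51–99% |
| equal expression, or no mean shift | – | 0% | 5% |

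**Step 3, does adjustment help?** A simulation (10,000 trials of 36 pairs, no within-cell change, SD of the change in neutrophil fraction 6 points, residual SD 0.25 on the log2 scale) compared the unadjusted paired t-test with the intercept from regressing the paired log2 difference on the paired change in neutrophil fraction. For a 5-point shift and expression in other cells 2, 3 or 5 times that in neutrophils, the unadjusted test rejected in 24%, 47% and 70% of trials. The adjusted test rejected in about 5% each time. With no mean shift both stayed at about 5%.

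**Step 4, cost in precision.** The adjusted effect is an intercept at zero change in mix. Before any gain from lower residual variance, its standard error is multiplied by about √(1 + (mean shift / SD of change)²). With an SD of 6 points:
- 5-point shift: √(1 + 25/36) = 1.30
- 10-point shift: √(1 + 100/36) = 1.94

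This is for one covariate. A second can leave the factor unchanged or raise it, but cannot lower it.

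**The case against.** The strongest reply is that the bias is hypothetical. It needs both a mean difference in cell mix and unequal expression across cell types, and the documents give data on neither. White blood cell count is listed beside liver, kidney and thyroid function in a broad panel, which is not evidence that a shift is expected. The two active conditions have the same content, and the post-intervention serum draw is fasted. For modest inputs, such as a twofold ratio and a 2-point shift, the error rate is barely above nominal. All of this stands, so the size can only be shown as a range.

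Two points of wording also stand. The protocol never uses the term whole blood; that is inferred from a directly drawn RNA tube with no separation step. Nor does it say that untransformed, unnormalised values will be tested; it is silent. Reference-gene normalisation in the laboratory remains possible, but would not by itself remove a cell-mix effect.

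A reader might go further and infer that a clock-gene difference should count as a clock effect only if it remains significant after adjustment. That does not follow. The cell mix is measured after the intervention, and the adjusted estimate loses precision exactly when the mix shifts, so a real within-cell effect could be discarded. Persistence would not prove a clock effect either: one RNA sample per intervention cannot separate a change in phase from a change in level.

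Finally, the gain from removing random variation in mix is small. Under the simulation inputs that variation raises the SD of differences by only 3%, 7% and 13% at ratios of 2, 3 and 5. The case for adjustment rests on a possible mean shift, not on noise.

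What the objections leave untouched is that the plan gives no means of separating cell mix from expression, although the data to examine it are collected.

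**Conclusion.** The point holds as a conditional weakness in the analysis of one exploratory secondary endpoint. The specimen, the matching differential and the absence of any specified adjustment are all in the text. Whether the comparison is actually biased is unknown. Under the stated assumptions the false-positive rate runs from 6–7% (twofold ratio, 2 points) to 51–99% (fourfold ratio, 10 points), and it is 5% if the mix does not shift on average or expression is equal across cell types.

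A reader might infer that the trial will report a spurious clock effect, or that its clock-gene result will be uninterpretable. The documents do not support that: they show neither a shift in mix nor unequal expression. The primary ISI comparison and the sample size are unaffected.

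**What to change.** In section 10.2, state that clock-gene expression is analysed on the log scale and keep the unadjusted paired difference. Add, as a pre-specified supportive analysis, a within-person model that includes the same-visit neutrophil and lymphocyte proportions. Report both estimates with confidence intervals, together with the between-condition difference in those proportions, and interpret them jointly. Do not require the effect to stay significant after adjustment. Fix this before the batch assay is run, so that the choice between estimates cannot depend on the results.

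The cost is a few sentences and one additional model; no new sample or visit is needed. The adjusted estimate will be less precise when the mix shifts (step 4 of the working), and it removes any part of the effect that acts through the cell mix. That is why it should stand beside the unadjusted estimate and not replace it.

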8.4 Withdrawal of individual subjects

Subjects can leave the study at any time for any reason if they wish to do so without any consequences. The investigator can decide to withdraw a subject from the study for urgent medical reasons.

8.4.1 Specific criteria for withdrawal (if applicable)

Not applicable

8.5 Replacement of individual subjects after withdrawal

If a subject withdraws from the study, the participant will not be replaced; the logistics of this study make it impossible to enter the study once it has started. We have taken this into account with the 10% drop-out rate.

8.6 Follow-up of subjects withdrawn from treatment

Not applicable

8.7 Premature termination of the study

Due to the COVID-19 pandemic and the consequential measures, this study could be postponed or temporally suspended. We aim to continue when possible and finish the study when all participants are included. To minimise the chance of premature termination of the study, the study duration will be relatively short.

9. SAFETY REPORTING

9.1 Temporary halt for reasons of subject safety

In accordance to section 10, subsection 4, of the WMO, the sponsor will suspend the study if there is sufficient ground that continuation of the study will jeopardise subject health or safety. The sponsor will notify the accredited METC without undue delay of a temporary halt including the reason for such an action. The study will be suspended pending a further positive decision by the accredited METC. The investigator will take care that all subjects are kept informed.

9.2 AEs, SAEs and SUSARs

9.2.1 Adverse events (AEs)

Adverse events are defined as any undesirable experience occurring to a subject during the study, whether or not considered related to [the investigational product / trial procedure/ the experimental intervention]. All adverse events reported spontaneously by the subject or observed by the investigator or his staff will be recorded with an exception for minor bruising due to the blood draw.

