5. TREATMENT OF SUBJECTS

5.1 Investigational treatment

5.1.1 Active morning and active evening intervention

Participants will participate in three interventions consisting each of a 14-day physical activity regimen. The active morning and active evening intervention are equal in content but in the active morning group, participants will be instructed to be active between 10:00 and 11:00 hour in the morning and the active evening will be instructed to be active between 19:30 and 20:30 in the evening. Both groups will be instructed to refrain from any moderate to vigorous exercise for the rest of the day. Per intervention, a total of eight Vitality Club training session will be organised given by a trained sports coach or physical therapist specialized in geriatric physical therapy. These training sessions will be different in character (e.g., a game of volleyball and a circuit training) but will all contain a combination of strength and endurance training tailored for older adults. Literature is inconclusive whether it is more beneficial to participate in aerobic endurance training (AET) or resistance exercise training (RET). AET is more beneficial for body composition and endurance and RET is more beneficial for muscle mass and strength. Both types of exercises contribute to important components of QOL and healthy ageing and therefore we believe that it is most valuable/effective to compose a training regimen containing both AET and RET exercises.(34) During the weekends (Saturday and Sunday), there will not be a Vitality Club sessions. Instead, participants will be asked to perform a 'relative rest' session. On a 'relative rest' day, participants will be given the opportunity to recover from the vitality club. Yet, since we do not want to lose the effect of the intervention, we ask the participants to perform any light activity during the given window of time of the intervention arm. For one weekend day (Saturday) in the measurement week, or when participants are unable to participate in the Vitality Club, they will be asked to perform some sort of physical activity/exercise at home (the 'Active@Home' program) between the above-mentioned times (depending on the intervention). Participants will be handed multiple training schedules/options for the Active@Home option corresponding to a metabolic equivalent of 3-8 MET's (moderate to vigorous physical activity) for one hour. Participants will also be asked to refrain from activities with equal MET's for the rest of the day to ensure that their physical activity peak will only be in the morning or evening (depending on the intervention). To ensure participants will stay well informed, they will be handed a booklet with all necessary information and a day by day description of all measurements and exercise program ('E4. Studieboekje').

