
5.1.1 Sedentary period

Literature shows that physical activity improves insomnia severity.(32) In previous studies, the follow-up period was at least 3 months. As we will use a shorter follow-up period in this study, we have included a sedentary period, to assess the effect of physical activity versus no physical activity. This intervention additionally examines the effect of physical activity timing. In order to verify that the exercise intervention provided in this study has a similar positive effect, we will compare our interventions to this sedentary period. All participants will start with a 14-day sedentary period. They will be instructed to refrain from any moderate to vigorous exercise. Compliance to these instructions will be observed through the wrist worn accelerometer. Where necessary, participants will be reminded of the instructions.

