9.5 Data Safety Monitoring Board (DSMB)

According the risk classification (K6.), this study has a negligible risk. Therefore we will not be appointing a DSMB.

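### Adverse events are recorded only if volunteered or observed, with no scheduled enquiry in any condition, so harms are likely to be under-recorded

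*Combined protocol and SAP*

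**What the plan says.** Section 9.2.1 defines an adverse event broadly, as any undesirable experience during the study whether or not related to it. It then sets the recording rule: "All adverse events reported spontaneously by the subject or observed by the investigator or his staff will be recorded", with minor bruising from the blood draw excepted. Sections 9.2.2 and 9.4 cover reporting of serious events and follow-up of events once known.

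The procedures in section 8.3 and the list in Appendix B contain no adverse-event question, checklist or diary. Section 10 contains no summary of adverse events.

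On contact with staff, section 5.1.1 (active interventions) says: "Per intervention, a total of eight Vitality Club training session will be organised given by a trained sports coach or physical therapist". It adds that "The active morning and active evening intervention are equal in content". It also says that "when participants are unable to participate in the Vitality Club, they will be asked to perform some sort of physical activity/exercise at home", and home exercise is planned for one Saturday in the measurement week.

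For the first condition, section 5.1.1 (sedentary period) says: "All participants will start with a 14-day sedentary period. They will be instructed to refrain from any moderate to vigorous exercise". On adherence it says: "Compliance to these instructions will be observed through the wrist worn accelerometer", with reminders where necessary. No coached sessions are described there.

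Section 9.5 appoints no DSMB because, under the risk classification, "this study has a negligible risk".

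**The concern.** The recording rule is passive. Participants are 60 to 80 years old and do hour-long strength and endurance sessions, some of them at home with no coach described. A strain or fall at home enters the record only if the participant volunteers it or somebody on the staff happens to notice its effects.

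At stake is the trial's description of harms. With no DSMB, no annual safety report and no other routine collection of harms described, the events recorded under 9.2.1 are the only routine harms data the trial will have. If those counts are low because nobody asked, they say little about whether the exercise programme was tolerated.

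A second, smaller issue is the opportunity to notice events. Coached contact is planned in the active periods and not in the sedentary period. A higher active-period count could then partly reflect who was being watched.

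**Working it through.** The plan states no adverse-event rate, reporting rate or safety power, so there is no figure to reproduce. The check is a count of contacts followed by two illustrations on stated assumptions.

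**1. Scheduled contacts per 14-day condition**

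| | Morning | Evening | Sedentary |
|---|---|---|---|
| Coached sessions (5.1.1) | up to 8 | up to 8 | 0 |
| End-of-period blood draw (8.3.4, Table 8.2) | 1 | 1 | 1 |
| Total of these | up to 9 | up to 9 | 1 |

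Eight is a maximum, because a missed session is replaced by home exercise. So at least 14 − 8 = 6 days of each active period have no coached session. The Summary also mentions assessment of well-being by a nurse at the centre and at home. It gives neither the frequency nor whether adverse events are asked about, so this is not counted.

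**2. What incomplete capture does with 40 participants**

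Let p be the true incidence per condition and r the share of affected participants whose event is recorded. Assume participants are independent. Then the expected number recorded = 40·p·r, and the chance of recording none = (1 − p·r)^40.

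For p = 10% (assumed):
- r = 100%: expected 4; 0.90^40 = 0.015
- r = 50%: expected 2; 0.95^40 = 0.129
- r = 25%: expected 1; 0.975^40 = 0.363

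Varying the assumed incidence:

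| p | r = 100% | r = 50% | r = 25% |
|---|---|---|---|
| 5% | 0.95^40 = 13% | 0.975^40 = 36% | 0.9875^40 = 60% |
| 10% | 1.5% | 13% | 36% |
| 20% | 0.80^40 = 0.01% | 0.90^40 = 1.5% | 0.95^40 = 13% |

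**3. Unequal contact with equal true risk**

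Let s be the chance of a spontaneous report, q the chance of detection at each contact, and k the number of contacts. Then P(recorded) = 1 − (1 − s)(1 − q)^k. Take k = 9 (active) and k = 1 (sedentary), which assumes that coaches' observations count and that all sessions are attended.

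- q = 0: the active/sedentary ratio is 1.00 for any s.
- s = 0.6, q = 0.05: active 1 − 0.4 × 0.95^9 = 0.748; sedentary 1 − 0.4 × 0.95 = 0.620; ratio 1.21.
- s = 0.3, q = 0.20: active 1 − 0.7 × 0.80^9 = 0.906; sedentary 1 − 0.7 × 0.80 = 0.440; ratio 2.06.

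Over s from 0.3 to 0.9 and q from 0 to 0.20 the ratio runs from 1.00 to 2.06. For morning versus evening, k is the same on both sides, so planned contact alone gives a ratio of 1.00.

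**The case against.** The strongest reply is that no planned analysis is affected. Adverse events are not a listed endpoint, no comparison of them is planned, the trial is classed as negligible risk on the basis of a separate document, and serious events and follow-up are covered. This is correct. It confines the point to the description of harms, but does not make a passive rule complete.

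Four stronger readings are tempting, and the documents do not support them.

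- *Harms are not comparable between any of the conditions.* Morning and evening share the same content, the same number of planned sessions and the same recording rule. Planned contact is balanced in the randomised primary contrast.
- *The sedentary period is watched only through the wristband.* It ends with a blood draw, the Summary describes nurse assessment of well-being, and the momentary assessments run five times a day in its measurement week. The accelerometer sentence concerns adherence, not safety. However, the momentary assessments cover mood, energy, cognition and sleep, not injuries or complaints.
- *Worse nights after evening exercise would be missed.* Sleep is what the trial measures. The ISI is completed at the end of each condition, and the sleep mat, the accelerometer and morning questions add to it.
- *Coaches' presence certainly raises active-period counts.* The protocol does not say whether the coach or physical therapist counts as the investigator's staff for recording events. The imbalance is conditional on that.

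It is also fair to say that the incidence and reporting rates used above are assumed, and that the proposed question would not equalise coached contact. Both stand.

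**Conclusion.** The point holds as a minor one about ascertainment. Followed exactly, section 9.2.1 yields only what is volunteered or noticed, and no adverse-event enquiry is described in any of the three conditions, so events are likely to be under-recorded. How far cannot be known from the documents. At an assumed 10% incidence, halving or quartering capture raises the chance of an empty record from 1.5% to 13% or 36%; the table shows how this moves with the assumed incidence.

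Active-versus-sedentary counts would in addition not be directly comparable if coaches' observations are recorded. The direction follows from the 8, 8 and 0 coached sessions; the size (1.00 to 2.06 in the illustration) depends on the assumed detection rates. That contrast is in any case confounded with time. No bias in a planned analysis is shown, and none between morning and evening.

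**What to change.** In section 9.2.1, have the research nurse ask one standard open question about new complaints or injuries since the last visit, at each existing end-of-period blood draw, in all three conditions. State whether coaches are to pass on what they see.

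Record the condition or washout in which each event began. This is needed because the recall windows differ: about 14 days at the end of the sedentary period (if baseline directly precedes it), and 7 + 14 = 21 days at the end of each active period, since a washout comes first.

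In section 10, tabulate events and participants with events by condition, descriptively, with a note that coached contact differs in the sedentary period and that this period is always first.

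The cost is about one minute at three existing contacts, one case record form field and one table. The downside is a few more minor events to record and follow. The question raises capture in every condition; it does not remove the difference in coached contact, which is why the table should stay descriptive.
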